10.2. Adverse Events Monitoring

All AEs regardless of seriousness or relationship to Medicinal Product (MP), spanning from the signature of the informed consent form, until the end of the study as defined by the protocol for that patient, are to be recorded on the corresponding page(s) included in the CRF and reported as described in the following sections.

For all adverse events, the investigator must pursue and obtain information adequate to determine the outcome of the adverse event and to assess whether it meets the criteria for classification as a serious adverse event requiring immediate notification to Sponsor or its designated representative.

For all adverse events, sufficient information should be obtained by the investigator to determine the causality of the adverse event. The investigator is required to assess causality. For adverse events with a causal relationship to the MP, Follow-Up by the investigator is required until the event or its sequelae resolve or stabilize at a level acceptable to the investigator, and Sponsor concurs with that assessment. This may imply that observations will continue beyond the last planned visit per protocol, and that additional investigations may be requested by the Monitoring Team up to as noticed by the sponsor

Whenever possible, diagnosis or single syndrome should be reported instead of symptoms. The Investigator should specify the date of onset, intensity, action taken with respect to MP, corrective treatment/therapy given, additional investigations performed, outcome and his/her opinion as to whether there is a reasonable possibility that the AE was caused by the MP.

10.3. Reporting Period

For serious adverse events, the reporting period to Sponsor or its designated representative begins from the time that the subject provides informed consent, which is obtained prior to the subject's participation in the study, i.e. prior to undergoing any study-related procedures and/or receiving MP, through and till the end of the Follow-Up Period as specified in the study protocol.

Any serious adverse event occurring any time after the reporting period must be promptly reported if a causal relationship to MP is SUSPECTED.

10.4. Severity Assessment

Study Protocol: EVA_CLEAR_11022017 Version Number: Final V2.0/19-Jun-2017

The severity of each AE and laboratory abnormality is to be assessed by the investigator according to following criteria

- Mild (Grade 1): AE or laboratory abnormality that is transient or is easily tolerated on continuation of study drug.
- Moderate (Grade 2): AE or laboratory abnormality that causes the patient discomfort and causes interference with the patient's usual activities.
- Severe (Grade 3): AE or laboratory abnormality that is incapacitating and causes considerable interference with the patient's usual daily activities, and/or may be life-threatening if it worsens.
- Life-Threatening (Grade 4): The AE or laboratory abnormality is life threatening as it exists (i.e., no worsening is required for the abnormality to be life-threatening).
- Death Related AE (Grade 5)

Note the distinction between the severity and the seriousness of an adverse event. A severe event is not necessarily a serious event. For example, a headache may be severe (interferes significantly with subject's usual function) but would not be classified as serious unless it met at ease one of the 6 seriousness criteria.

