7.2. Data Collection

	Data Collection Schedule					
Data to be collected	Visit 1 (Baseline)	Visit 2 (Week 6)	Visit 3 (Week 12)	Visit 4 (Week 20)	Visit 5 (Week 28)	Visit 6 (Week 36)
Informed consent	Х					
Inclusion/ Exclusion	Х					
Physical Examination/ Vital Signs ¹	х	х	х	х	х	х
Demographics	Х					
Smoking Status	Х					
Alcohol Consumption	Х					
Medical history	Х					
Gynecological History (FEMALES ONLY)	х					
Concomitant Medications	х	х	x	x	х	х
RA History ²	Х					
Disease Assessment ³	Х	Х	Х	Х	Х	х
Laboratory Tests ⁴	Х	Х	Х	Х	Х	Х
Health Assessment Questionnaire (HAQ Disability Index) ⁵	x	х	x	x	х	x
Poor Prognostic Factors ⁶	х					
Adverse Events & Serious Adverse Events		Х	Х	х	Х	Х
Study Completion Form						X
1: Physical Examination/Vitals S	ians: Heiaht will be	collected in V1 c	only			

7.2.1.Data Collection Schedule

2: Rheumatoid Arthritis History will include RA Duration, Previous/Current therapies including duration, dose, adverse events/serious adverse events experienced during previous treatment and Reason for starting Leflunomide* (previous DMARDs failure, insufficient response, allergy, intolerance, side effects) *dose (if the patient received loading dose or not) and Previous X-RAY reports.

3: Disease Assessment will be done by Clinical Disease Activity Index (CDAI).

4: Laboratory Tests include CBC, ESR assessed by Westergren method (First hour), C-reactive protein (titer), AST, ALT, Sr Cr, Sr ACPA, Sr RF titer, FBG, HBsAg and HCV-Ab.

Study Protocol: EVA_CLEAR_11022017

5: Stanford University-Health Assessment Questionnaire (HAQ Disability Index).
 6: Poor prognostic factors: Presence of 1 or more of; Bony erosions by radiograph, High swollen joint count, Extra-articular disease (nodules, vasculitis, Felty's syndrome), Functional limitation (HAQ), High disease activity as measured by composite indices (DAS28, SDAI and/or CDAI), High acute phase reactants (CRP and ESR) or High RF and/or anti-CCP.

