10.1.7. Abnormal Test Findings

Treatment-emergent laboratory test abnormalities considered to be of clinical concern should be recorded as AEs in the CRF

The criteria for determining whether an abnormal objective test finding should be reported as an adverse event are as follows:

- 1. Test result is associated with accompanying symptoms, and/or
- 2. Test result requires additional diagnostic testing or medical/surgical intervention, and/or

Study Protocol: EVA_CLEAR_11022017 Versi

- 3. Test result leads to a change in study dosing or discontinuation from the study, significant additional concomitant drug treatment, or other therapy, and/or
- 4. Test result is considered to be an adverse event by the investigator or sponsor.

Merely repeating an abnormal test, in the absence of any of the above conditions, **does not** constitute an adverse event.

Any abnormal test result that is determined to be **an error** does not require reporting as an adverse event.

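### Section 10.4 grades laboratory abnormalities by tolerability and function with no value thresholds, so the recorded severity need not track the size of the abnormality

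*Combined protocol and SAP*

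**What the plan says.** Section 10.4 puts clinical events and laboratory findings on one five-level scale: "The severity of each AE and laboratory abnormality is to be assessed by the investigator according to following criteria". The levels are:

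- Grade 1 (mild): "AE or laboratory abnormality that is transient or is easily tolerated on continuation of study drug".
- Grade 2 (moderate): "AE or laboratory abnormality that causes the patient discomfort and causes interference with the patient's usual activities".
- Grade 3 (severe): incapacitating with marked disruption of daily life, "and/or may be life-threatening if it worsens".
- Grade 4: life-threatening already, with the clarification that "no worsening is required for the abnormality to be life-threatening".
- Grade 5: a death-related event.

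No level cites a laboratory value, a multiple of a reference limit or a cell count.

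Section 10.1.7 decides when a result becomes an AE: "Treatment-emergent laboratory test abnormalities considered to be of clinical concern should be recorded as AEs in the CRF". Its four criteria contain no numeric threshold and do not set a grade.

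The relevant data are planned. Footnote 4 to the schedule in section 7.2.1 reads "Laboratory Tests include CBC, ESR assessed by Westergren method (First hour), C-reactive protein (titer), AST, ALT, Sr Cr" and goes on to further tests. The schedule marks laboratory tests at all six visits, although the visit overview in the Synopsis qualifies some laboratory data as collected only if applicable.

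Section 10.2 asks the investigator to record intensity for AEs. Section 10.1.2 states that no AEs of special interest will be collected. The Synopsis lists 24 private-clinic sites and gives the central laboratory as not applicable.

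**The concern.** A scale built on how the patient feels and functions suits clinical events. It suits laboratory findings poorly, because a patient can have a marked rise in liver enzymes or fall in blood counts without noticing anything. If the grade does not use the measured value, a small and a large abnormality can carry the same label, and two equal abnormalities can carry different labels.

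The safety profile is a secondary objective (section 5.3), and liver enzymes, creatinine and blood counts are among its main planned data. With no AEs of special interest, there is no separate hepatic or haematological category to show what the grade misses. At stake is whether a reader of the safety results can take laboratory severity at face value.

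**Working it through.** The documents give no figure on this point, so there is nothing to recalculate. The check is to take one test case, a large abnormality in AST/ALT, creatinine or CBC in a patient without symptoms, and read it against each level of section 10.4.

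| Level | What it requires | Can the test case meet it? |
|---|---|---|
| Grade 1 | Transient, or easily tolerated on continued drug; either is enough | Yes, whatever the size |
| Grade 2 | Discomfort and interference with activities; both | No, by definition |
| Grade 3, first limb | Incapacitating, with considerable interference | No |
| Grade 3, second limb | Could become life-threatening on worsening | Yes, if the investigator so judges |
| Grade 4 | Life-threatening as it stands | Yes, if the investigator so judges |

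Four consequences follow.

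1. **Missing middle.** The available outcomes are Grade 1, or Grade 3 or 4. A symptom-free abnormality can never be moderate.
2. **Overlap.** A large transient rise can meet Grade 1 (transient) and Grade 3 (dangerous if it worsened) together. Section 10.4 does not say which prevails.
3. **Gap.** A symptom-free abnormality that persists, leads to the drug being stopped and is not judged potentially life-threatening fits no level cleanly. It would still be recorded as an AE, because section 10.1.7 counts a result that leads to a dosing change or discontinuation.
4. **Between-site variation.** Grade 1 or Grade 3 is decided by individual judgement at 24 sites, with no numeric anchor and no central laboratory. The same value can properly be graded 1 at one site and 3 at another.

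The next question is where the grade is used.

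- Safety endpoint (section 8.4.3): frequency of AEs/SAEs and relation to the drug. Severity is not named.
- AE recording (section 10.1.7): does not use the grade.
- Seriousness (section 10.1.3 and the closing note of 10.4): separate from severity. Blood dyscrasias without hospitalization are an example of an important medical event.
- Interim review (section 8.7.3): safety and efficacy, with ongoing monitoring of SAEs. Severity is not mentioned.
- Descriptive analysis (section 8.7.1): percentages for all categorical variables. That wording would cover a recorded grade, but no severity table is specified.

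The weakness therefore lies in a grade that the protocol asks investigators to collect, and it does not carry into the named endpoint.

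**The case against.** The best defence is that section 10.4 does not ignore silent toxicity. The second limb of Grade 3 and all of Grade 4 need no symptoms, and an investigator could well judge a large enzyme rise or count fall dangerous if it worsened. Grade 1 is not a default either: no sentence sends an abnormality there because it fits nowhere else. Large values need not be hidden, since the tests are scheduled through follow-up and section 8.7.1 describes continuous variables with their minimum and maximum.

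All of this is right, and it rules out three stronger readings that a reader might infer.

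- *Every large symptom-free abnormality is recorded as mild.* The text allows this but does not require it.
- *The monitoring committee and the final report will receive an understated severity table.* No section specifies such a table for either.
- *A definite number of patients is misgraded.* One could multiply the 400 planned patients by an assumed 2% to 10% rate of such abnormalities (400 × 0.02 = 8; 400 × 0.10 = 40). The rate is not in the documents, and the product would also require every case to be graded 1, which the Grade 3 limb contradicts.

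What the defence does not answer is the lack of any value-based anchor, the unreachable Grade 2, the overlap of Grades 1 and 3, and the gap. The symptom-free limbs leave the outcome to unaided judgement. Section 8.7.1 does not name laboratory values, so their summary is possible but not promised.

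**Conclusion.** The point holds as a weakness in how laboratory severity is graded. Under section 10.4 a large symptom-free abnormality can be mild, cannot be moderate, and is severe or worse only on the investigator's judgement of present or potential threat to life. The grade need not follow the size of the abnormality and may differ between sites for the same value.

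The effect is confined to the severity part of the safety profile. It does not touch the primary endpoints, the named safety endpoint, which results become AEs, or which AEs are serious. Its numerical size cannot be estimated from the documents, and its direction is not fixed: downgrading of silent abnormalities is possible, but so is plain inconsistency.

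The conclusion assumes that no value-based laboratory scale exists in a document outside those reviewed, such as the CRF or its completion instructions. The change is worth making because the protocol requires intensity to be recorded and the values that would support a better grade are already scheduled.

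**What to change.** In section 10.4, limit the present scale to clinical AEs. For laboratory results:

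- name one published value-based toxicity scale and fix it, with its version, before the first analysis, which here is the interim analysis after Visit 3;
- derive the grade by program from the recorded AST, ALT, creatinine and CBC values;
- capture each local laboratory's reference limits and units, if the CRF does not already do so;
- tabulate the derived grades by visit as shifts from baseline, alongside the AE tables.

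No cut-offs are proposed here, because the documents give none; they should come from the named scale. The change concerns reporting only and sets no rule for dosing or stopping treatment.

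The cost is about one paragraph of protocol text, possibly a few CRF fields, and modest data entry and programming. No new tests or visits are needed. The sponsor should expect that the reported severity profile may look less favourable.

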10.5. Causality Assessment

The investigator's assessment of causality must be provided for all adverse events (Serious and Non-Serious); the investigator must record the causal relationship in the CRF, as appropriate, and report such an assessment in accordance with the serious adverse reporting requirements if applicable. An investigator's causality assessment is the determination of whether there exists a reasonable possibility that MP caused or contributed to an adverse event. If the investigator's causality assessment is "unknown but not related to MP", this should be clearly documented on study records.

In addition, if the investigator determines a serious adverse event is associated with study procedures, the investigator must record this causal relationship in the source documents and CRF, as appropriate, and report such an assessment in accordance with the serious adverse event reporting requirements, if applicable.

10.5.1. WHO-UMC Causality Categories

Causality Ass Term	essment Criteria
-----------------------	------------------

Causality Term	Assessment Criteria
Certain	 Event or laboratory test abnormality, with plausible time relationship to drug intake Cannot be explained by disease or other drugs Response to withdrawal plausible (pharmacologically, pathologically) Event definitive pharmacologically or phenomenologically (i.e. an objective and specific medical disorder or a recognized pharmacological phenomenon) Rechallenge satisfactory, if necessary
Probable / Likely	 Event or laboratory test abnormality, with reasonable time relationship to drug intake Unlikely to be attributed to disease or other drugs Response to withdrawal clinically reasonable Rechallenge not required
Possible	 Event or laboratory test abnormality, with reasonable time relationship to drug intake Could also be explained by disease or other drugs Information on drug withdrawal may be lacking or unclear
Unlikely	 Event or laboratory test abnormality, with a time to drug intake that makes a relationship improbable (but not impossible) Disease or other drugs provide plausible explanations
Conditional/Unc lassified	 Event or laboratory test abnormality More data for proper assessment needed, or Additional data under examination
Unassessable/ Unclassified	 Report suggesting an adverse reaction Cannot be judged because information is insufficient or contradictory Data cannot be supplemented or verified

10.6. Exposure During Pregnancy

For Investigational Products and for Marketed Products, an exposure during pregnancy (also referred to as Exposure In-Utero [EIU]) occurs if:

 A female becomes, or is found to be, pregnant either while receiving or having been directly exposed to the Investigational Product(e.g., environmental exposure), or the female becomes, or is found to be, pregnant after discontinuing and/or being directly exposed to the Investigational Product (maternal exposure).

2. A male has been exposed, either due to treatment or environmental, to the Investigational Products prior to or around the time of conception and/or is exposed during his partner's pregnancy (paternal exposure).

If any study subject or study subject's partner becomes or is found to be pregnant during the study subject's treatment with the Medicinal Product, the investigator must submit this information to the Sponsor.

This must be done irrespective of whether an adverse event has occurred and within 24 hours of awareness of the pregnancy.

The information submitted should include the anticipated date of delivery.

Follow-up is conducted to obtain pregnancy outcome information on all Exposure during pregnancy reports with an unknown outcome. The investigator will follow the pregnancy until completion or until pregnancy termination (i.e., induced abortion) and then notify the Sponsor of the outcome. The investigator will provide this information as a follow up to the initial Exposure in Utero Pregnant Form. The reason(s) for an induced abortion should be specified.

An EIU report is NOT created when an ectopic pregnancy report is received since this pregnancy is not usually viable. Rather, a serious adverse event case is created with the event of ectopic pregnancy.

If the outcome of the pregnancy meets the criteria for immediate classification as a serious adverse event (i.e., spontaneous abortion, stillbirth, neonatal death, or congenital anomaly [Including that in an aborted fetus, stillbirth or neonatal death]), the investigator should follow the procedures for reporting serious adverse events.

In the case of a live birth, the "normality" of the newborn can be assessed at the time of birth (i.e., no minimum follow-up period of a presumably normal infant is required before an Exposure in Utero Pregnant Form can be completed).

The "normality" of an aborted fetus can be assessed by gross visual inspection, unless preabortion test findings are suggestive of a congenital anomaly.

Additional information about pregnancy outcomes that are classified as serious adverse events follows:

- 1. Spontaneous abortion; includes miscarriage and missed abortion.
- All neonatal deaths that occur within 1 month of birth should be reported, without regard to causality, as serious adverse events. In addition, any infant death after 1 month that the investigator assesses as possibly related to the exposure during pregnancy to the investigational medication should be reported.

Additional information regarding the exposure during pregnancy may be requested by the investigator. Further follow-up of birth outcomes will be handled on a case-by-case basis (e.g. follow-up on preterm infants to identify developmental delays).

10.7. Withdrawal Due to Adverse Events

Withdrawal due to adverse event should be distinguished from withdrawal due to Insufficient Response, according to the definition of adverse event noted earlier, and recorded on the appropriate Adverse Event CRF Page.

When a subject withdraws due to a serious adverse event, the serious adverse event must be reported in accordance with the reporting requirements defined below.

10.8. Eliciting Adverse Event Information

A consistent methodology of non-directive questioning should be adopted for eliciting adverse event information at all patient evaluation time points.

Examples of non-directive questions include the following:

- "How have you felt since your last clinic visit?"
- "Have you had any new or changed health problems since you were last here?"

10.9. Procedures for Recording Adverse Events

Investigators should use correct medical terminology/concepts when recording adverse events on the Adverse Event CRF. Avoid colloquialisms and abbreviations.

Only one adverse event term should be recorded in the event field on the Adverse Event Form.

10.10. Reporting Requirements

10.10.1.General Instructions

Investigators will seek information on adverse events at each patient contact.

All adverse events, whether reported by the patient or noted by study personnel, will be recorded in the patient's medical record and on the Adverse Event Form in CRF.

After prescription of MP, all adverse events, regardless of relationship to study drug, will be reported.

Each adverse event is to be assessed to determine if it meets the criteria for serious adverse events. If a serious adverse event occurs, expedited reporting will follow local and international regulations, as appropriate.

10.10.2. Reporting of Serious Adverse Event

If a serious adverse event occurs, Sponsor or its representative is to be notified within 24 HOURS OF AWARENESS OF THE EVENT by the investigator or delegate on behalf. In particular, if the serious adverse event is fatal or life-threatening, notification to Sponsor or its representative must be made IMMEDIATELY, irrespective of the extent of available adverse event information.

This timeframe also applies to additional new information (Follow-Up) on previously forwarded serious adverse event reports as well as to the initial and follow-up reporting of Exposure during pregnancy cases.

In the rare event that the investigator does not become aware of the occurrence of a serious adverse event immediately (e.g., if an outpatient study subject initially seeks treatment elsewhere), the investigator is to report the event within 24 hours after being aware of it and document the time of his/her first awareness of the adverse event.

For all serious adverse events, the investigator is obligated to pursue and provide information to Sponsor or its representative in accordance with the timeframes for reporting specified above. In addition, an investigator may be requested by Sponsor or its representative to obtain specific additional follow-up information in an expedited fashion.

In general, this information will include a description of the adverse event in sufficient detail to allow for a complete medical assessment of the case and independent determination of possible causality. Information on other possible causes of the event, such as concomitant medications and illnesses must be provided. In the case of a subject death, a summary of available autopsy findings must be submitted as soon as possible to Sponsor or its representative or its designated representative.

